11.7.7.2 Pregnancy

Subjects will be counseled to inform the investigator of any pregnancy that occurs during study treatment and for 90 days after the last dose of study drug.

If a female subject or the female partner of a male subject becomes pregnant while participating in the study, study drug will be permanently discontinued immediately. The investigator will notify the medical monitor and Vertex GPS within 24 hours of the site's knowledge of the subject's (or partner's) pregnancy using the Pregnancy Information Collection Form.

If confirmed to be on active drug, the subject or partner will be followed until the end of the pregnancy and the infant will be followed for 1 year after the birth, provided informed consent is obtained. A separate ICF will be provided to explain these follow-up activities. Pregnancy itself does not constitute an AE.

12 STATISTICAL AND ANALYTICAL PLANS

12.1 Sample Size and Power

12.1.1 Primary Objectives

The primary objectives of the study are the evaluation of safety and tolerability, and efficacy of [REDACTED] VX-440 in TC with TEZ/IVA (all parts). The sample size calculations described below are deemed adequate to evaluate the objectives of the study, based on clinical and statistical considerations.

12.1.1.1 Safety and Tolerability

The primary safety endpoint is the incidence of AEs. Approximately 198 subjects will be enrolled in the study with approximately 160 subjects receiving VX-440 [REDACTED] or triple combination with IVA and/or TEZ. The sample size for each treatment group will provide sufficient data for a descriptive analysis of AEs. Table 12-1 provides the probability of observing an AE in at least 1 subject based on sample sizes ranging from 10 to 50 subjects per treatment group and AE incidences ranging from 5% to 15%. The probability calculations are based on a binomial model using the probability calculator in the PASS software package (Version 11.0).

Table 12-1 Probability of Observing an Adverse Event

AE Incidences ^a	Number of Subjects per Treatment Group ^b				
	10	20	30	40	50
5%	40%	64%	79%	87%	92%
10%	65%	88%	96%	98%	>99%
15%	80%	96%	>99%	>99%	>99%

AE: adverse event

^a AE incidences are based on 4 weeks of treatment in Parts 1 and 2, [REDACTED]

^b Applies to Parts 1 [REDACTED]

12.1.1.2 Efficacy

The primary efficacy endpoint is the absolute change from baseline in ppFEV₁ through Day 29 in Parts 1 and 2, [REDACTED]. Table 12-2 provides the power to reject the null within-group hypothesis of no difference in the mean absolute change from baseline for ppFEV₁ through Day 29 or Week 12, as applicable, for any treatment group in Parts 1, 2, [REDACTED] with a sample size ranging from 8 to 44 subjects per treatment group. The power calculations are based on a 2-sided 1-sample *t*-test at alpha = 5% using the PASS software package (Version 11.0), assuming an absolute mean change of 3 to 7 percentage points and an SD of 8 percentage points in the absolute change from baseline for ppFEV₁. Sample sizes of 16 to 44 subjects per treatment group provide adequate power for mean changes of 5 to 7 percentage points as expected in Parts 1, 2, [REDACTED].

Table 12-2 Power for Within-group Difference for Mean Absolute Change From Baseline in ppFEV₁

Mean Absolute Change From Baseline in ppFEV ₁	Number of Subjects per Treatment Group ^a							
	8	16	20	22	24	40	42	44
3%	15%	29%	36%	39%	42%	64%	66%	68%
4%	23%	46%	56%	61%	65%	87%	89%	90%
5%	33%	65%	76%	80%	83%	97%	98%	98%
6%	45%	80%	89%	92%	94%	>99%	>99%	>99%
7%	57%	90%	96%	97%	98%	>99%	>99%	>99%

ppFEV₁: forced expiratory volume in 1 second; SD: standard deviation

Note: An SD of 8 percentage points for the absolute change from baseline in ppFEV₁ was used for power calculations.

^a Applies to Parts 1 [REDACTED]

12.1.2 Secondary Objectives

A secondary objective of the study is the evaluation of the PD effect of VX-440 in TC with TEZ/IVA (all parts) [REDACTED].

12.1.2.1 Pharmacodynamic Effect (Part 1)

The absolute change from baseline through Day 29 in sweat chloride is a secondary endpoint used to evaluate the PD objective of the study. In Part 1, a test for a decreasing dose-response trend between placebo and the TC dose groups will be performed using a multiple comparisons procedure (MCP). The procedure consists of testing the null hypothesis of the lack of a decreasing dose-response trend versus a decreasing trend using the 1-sided maximum *t*-statistic that controls the type I error at alpha = 5%. The procedure requires a family of candidate dose-response models to be prespecified, that covers the range of plausible and diverse dose-response profiles.

The candidate models that best describe the expected decreasing dose-response profile of the TC groups compared to placebo include a linear model, a maximum effect (E_{max}) model, and a sigmoid E_{max} model. The contrasts (i.e., linear combinations of the treatment group means through Day 29) selected to perform the MCP and that capture the shape of these candidate models are described in Table 12-3 below.

Table 12-3 Contrast Coefficients for the Multiple Comparisons Procedure in Part 1, Cohort 1B

Candidate Model	Placebo	TC-1B-low	TC-1B-high
Linear	1.0	0.0	-1.0
E _{max}	1.0	-0.5	-0.5
Sigmoid E _{max}	0.5	0.5	-1.0

E_{max}: maximum effect; TC: triple combination

Table 12-4 provides the power to detect a dose-response trend with the MCP procedure for 3 different expected dose-response profiles with a total sample size of 32 subjects in Cohort 1B assigned to TC-1B-high, TC-1B-low, and placebo in the ratio 2:1:1, based on 5000 simulations for each profile using the MCPMod R software package [Version 1.0-8].

Table 12-4 Power to Detect a Dose-response Trend Based on Change From Baseline in Sweat Chloride in Part 1, Cohort 1B

Candidate Model	Mean Change From Baseline in Sweat Chloride			Power
	Placebo	TC-1B-low	TC-1B-high	
Linear	0	-15	-20	95%
Sigmoid E _{max}	0	0	-20	99%
E _{max}	0	-20	-20	96%

E_{max}: maximum effect; TC: triple combination

Note: A 1-sided maximum *t*-statistic with a sample size of 32 subjects in Cohort 1B assigned to TC-1B-high, TC-1B-low, and placebo at a ratio 2:1:1 was used for power calculations. An SD change from baseline in sweat chloride of 13 mmol/L was used for power calculations.

Table 12-5 provides the power to reject the null within-group hypothesis of no difference in the mean absolute change from baseline for sweat chloride through Day 29 (Parts 1 and 2) [REDACTED] for any treatment group with a sample size ranging from 8 to 44 subjects per treatment group. The power calculations are based on a 2-sided 1-sample *t*-test at alpha = 5% using the PASS software package (Version 11.0), assuming a mean change of -10 to -20 mol/L and an SD of 13 mmol/L in the absolute change from baseline for sweat chloride.

Table 12-5 Power for Within-group Difference for Mean Absolute Change From Baseline in Sweat Chloride

Mean Absolute Change From Baseline in Sweat Chloride (mmol/L)	Number of Subjects per Treatment Group ^a							
	8	16	20	22	24	40	42	44
-10	47%	82%	90%	93%	95%	>99%	>99%	>99%
-12	61%	93%	97%	98%	99%	>99%	>99%	>99%
-15	80%	99%	>99%	>99%	>99%	>99%	>99%	>99%
-18	92%	>99%	>99%	>99%	>99%	>99%	>99%	>99%
-20	96%	>99%	>99%	>99%	>99%	>99%	>99%	>99%

SD: standard deviation

Note: An SD of 13 mmol/L for the absolute change from baseline in sweat chloride was used for power calculations.

^a Applies to Parts 1 [REDACTED]

12.2 Analysis Sets

The following analysis sets are defined: All Subjects Set, Full Analysis Set, and Safety Set. Additional analysis sets related to the Run-in Period in Part 2 will be defined in the statistical analysis plan, as appropriate.

The **All Subjects Set** will include all subjects who were randomized or received at least 1 dose of study drug. This analysis set will be used for all individual subject data listings and disposition summary tables, unless otherwise specified.

The **Full Analysis Set (FAS)** will include all randomized subjects who have received at least 1 dose of study drug in the Treatment Period. The FAS will be used to summarize subject demographics and baseline characteristics, and for all PD and efficacy analyses, unless otherwise specified.

The **Safety Set** will include all subjects who received at least 1 dose of study drug in the Treatment Period. The Safety Set will be used for all safety analyses, unless otherwise specified.

12.3 Statistical Analysis

This section presents a summary of the planned statistical analyses of the primary PD and efficacy endpoints of the study. Statistical analysis details will be provided in the statistical analysis plan (SAP) and clinical pharmacologic analysis details will be provided in the clinical pharmacology analysis plan (CPAP). Both plans will be finalized before the clinical data lock and unblinding of the study.

12.3.1 General Considerations

Continuous variables will be summarized using the following descriptive summary statistics: the number of subjects (n), mean, SD, standard error (SE), median, minimum value (min), and maximum value (max). The precision of the measurement for each continuous variable will be specified in the SAP. Unless otherwise specified, minimum and maximum values will be reported with the same precision as the units of the raw data. The mean, median, SD, and SE will be reported to 1 additional decimal place. Any values that require a transformation to standard units (metric or International System [SI]) will be converted with the appropriate precision.

Categorical variables will be summarized using counts and percentages. Percentages will be presented to 1 decimal place.

The **baseline** value, unless otherwise specified, will be defined as the most recent non-missing measurement (scheduled or unscheduled) collected before the first dose of study drug in the Treatment Period (i.e., Day 1). For ECG, baseline will be defined as the average of the most recent triplicate pretreatment measurements before the first dose of study drug in the Treatment Period (i.e., Day 1).

Absolute change from baseline will be calculated as postbaseline value – baseline value.

Relative change from baseline will be calculated as (postbaseline value – baseline value)/baseline value.

The Treatment-emergent (TE) Period will include the time from the first dose in the Treatment Period to the Safety Follow-up Visit or 28 days after the last dose of the study drug for subjects who do not complete the Safety Follow-up Visit. Additional TE periods related to the Run-in Period for Part 2 will be defined in the SAP, as appropriate.

There will be no multiplicity adjustment for performing multiple hypothesis tests.

The rules for handling missing data due to treatment or study discontinuation will be described in the SAP.

All data will be summarized for Parts 1, 2, [REDACTED] separately, unless specified otherwise.

12.3.2 Background Characteristics

12.3.2.1 Subject Disposition

The number and percentage of subjects in each disposition category (e.g., randomized, included in the FAS, included in the Safety Set, completed Treatment Period, completed study/Safety Follow-up Visit, and discontinued treatment or study with a breakdown of the reasons for discontinuation) will be summarized overall and by treatment group.

12.3.2.2 Demographics and Baseline Characteristics

Demographic, background (e.g., medical history), and baseline characteristics will be summarized using descriptive summary statistics.

The following demographics and baseline characteristics will be summarized overall and by treatment group for the FAS and will include (but are not limited to): sex, race, age, baseline weight, baseline height, baseline BMI, baseline ppFEV₁, and baseline sweat chloride.

No statistical tests will be performed to evaluate baseline imbalance between treatment groups.

12.3.2.3 Prior and Concomitant Medications

Medications used in this study will be coded using the World Health Organization Drug Dictionary Enhanced and categorized as the following:

- **Prior medication:** any medication that started before initial dosing of study drug, regardless of when it ended
- **Concomitant medication:** medication continued or newly received during the TE Period
- **Post-treatment medication:** medication continued or newly received after the TE Period

A given medication may be classified as a prior medication, a concomitant medication, or a post-treatment medication; both prior and concomitant; both concomitant and post-treatment; or prior, concomitant, and post-treatment. If a medication has a missing or partially missing start/end date or time and if it cannot be determined whether it was taken before the first dose of study drug, concomitantly during the TE Period, or after the TE Period, it will be considered in all 3 categories of prior, concomitant, and post-treatment medication.

Prior medications and concomitant medications will be summarized descriptively by Preferred Name based on the FAS. Post-treatment medications will be provided separately in an individual subject data listing.

Additional classifications of concomitant medications related to the Run-in Period will be defined in the SAP, as appropriate.

12.3.2.4 Study Drug Exposure and Compliance

Exposure to study drug will be summarized for the FAS in terms of duration of treatment a subject received (in days), defined as the last day minus the first day of study drug plus 1.

Dosing compliance based on number of pills taken, will be summarized for the FAS, and will be derived as $100 \times [(total\ number\ of\ pills\ dispensed) - (total\ number\ of\ pills\ returned)] / (total\ number\ of\ pills\ planned\ to\ be\ taken\ per\ day \times duration\ of\ study\ drug\ exposure\ in\ days)$.

Dosing compliance based on study drug exposure, will be derived as $100 \times [1 - (total\ number\ of\ days\ of\ study\ drug\ interruption) / (duration\ of\ study\ drug\ exposure\ in\ days)]$.

12.3.2.5 Important Protocol Deviations

An important protocol deviation (IPD) is a deviation that may significantly affect the completeness, accuracy, or reliability of the study data or that may significantly affect a subject's rights, safety, or well-being. The rules for identifying an IPD will be described in the SAP.

All IPDs will be provided in an individual subject data listing.

12.3.3 Efficacy Analysis

A coprimary objective of the study is the evaluation of the efficacy of [REDACTED] VX-440 in TC with TEZ/IVA (all parts).

12.3.3.1 Analysis of Primary Efficacy Variables

The primary efficacy variable is the absolute change from baseline for ppFEV₁ through Day 29 in Parts 1 and 2, [REDACTED]. The analysis will be performed using a mixed-effects model for repeated measures (MMRM) with change from baseline as the dependent variable. [REDACTED]

[REDACTED] stratification factors at randomization as categorical covariates, when applicable. The model will be estimated using restricted maximum likelihood. Denominator degrees of freedom for the F test for fixed effects will be estimated using the Kenward-Roger approximation. A compound symmetry covariance structure will be used to model the within-subject errors. Conditional on fixed effects, missing data due to treatment or study discontinuation will be assumed to be missing at random.

Descriptive analyses of the change from baseline will be performed for all treatment groups in Parts 1, 2, [REDACTED]. Adjusted means and 95% confidence intervals of the average treatment effects through Day 29 or Week 12, as applicable, with 2-sided *P* values, will be estimated within MMRM using LSMeans via PROC MIXED in SAS, for all within-group and between-group comparisons in all parts.

[REDACTED]

Further, relevant data from Parts 1, 2, [REDACTED] will be pooled as appropriate within MMRM with appropriate adjustment for covariates. Details will be provided in the SAP.

[REDACTED]

There will be no multiplicity adjustment for performing multiple hypothesis tests.

12.3.3.2 Analysis of Secondary Efficacy Variables

The secondary efficacy variables include:

- Relative change in ppFEV₁ from baseline through Day 29 (Parts 1 and 2) and [REDACTED]
- Absolute change in the CFQ-R respiratory domain score from baseline at Day 29 (Parts 1 and 2) [REDACTED]

- [REDACTED]
- [REDACTED]
- [REDACTED]
- [REDACTED]
- [REDACTED]

Details of the analysis will be provided in the SAP.

[REDACTED]

12.3.4 Pharmacodynamic Analysis

A secondary objective of the study is the evaluation of the PD effect on sweat chloride concentrations of [REDACTED] VX-440 in TC with TEZ/IVA (all parts).

12.3.4.1 Pharmacodynamic Effect

The absolute change in sweat chloride from baseline through Day 29 is a secondary endpoint used to evaluate the PD objective of the study. The test to detect a decreasing dose-response trend of VX-440 at 2 doses in TC with TEZ/IVA relative to placebo based on sweat chloride, will be performed using the MCP procedure with the prespecified comparisons (contrasts) of the treatment group means within a linear MMRM framework. The model will include treatment group, visit, and treatment-by-visit interaction as fixed effects, with the ppFEV₁ stratification factor at randomization as a categorical covariate. The test will be performed using the 1-sided maximum *t*-statistic of the individual *t*-statistics for the multiple prespecified contrasts at alpha = 5%, based on the treatment group means through Day 29 in Cohort 1B.

[REDACTED]

Adjusted means and 95% confidence intervals of the average treatment effects through Day 29 or Week 12, as applicable, with 2-sided *P* values, for all within-group and between-group

comparisons in all parts will be estimated within MMRM, with appropriate adjustment for covariates.

Additional details of the analysis will be provided in the SAP.

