In vitro data indicate that maintaining adequate IVA exposure in vivo will be important for maximizing efficacy of the TC. When administered in combination with VX-440 200 mg, the dose of IVA will be the same as the recommended dose for IVA monotherapy for patients aged 12 years and older (150 mg q12h). Preliminary data from Study 002 indicate that VX-440 is a moderate to strong inducer of CYP3A4. Because IVA is a sensitive CYP3A substrate, the dose of IVA will be increased from 150 mg q12h to 300 mg q12h when it is administered with VX-440 at a dose level of 600 mg q12h. These dose levels were evaluated in Study 002 and were safe and well tolerated. At these dose levels, IVA exposure was approximately 50% lower relative to IVA 150 mg q12h monotherapy based on historical data.¹² If the high dose of VX-440 is reduced to 400 mg q12h, the IVA dose will remain 300 mg q12h, as VX-440 induction is predicted to be similar in magnitude at this dose relative to 600 mg q12h. Phase 3 and post-approval data for IVA monotherapy have not revealed any systemic exposure-related safety findings and indicate a wide therapeutic margin for safety. Use of a higher IVA dose when coadministering IVA with a CYP3A inducer is consistent with the approach for combination therapy with LUM (a strong CYP3A inducer). In that combination therapy, the IVA dose is 250 mg q12h.

Treatment Duration

The 4-week treatment duration in Parts 1 and 2 is based on previous experience with CF correctors and potentiators in clinical studies of subjects with CF. Based on preliminary data from Studies 001 and 002, and data from previous studies of TEZ and IVA, all components of the TC reach steady-state levels of exposure by 2 to 3 weeks. In previous studies of TEZ and IVA, PD effects were observed within 4 weeks of treatment. In Study VX06-770-101, treatment with IVA for 28 days resulted in statistically significant within-group changes from baseline in ppFEV₁ as well as a trend toward clinically meaningful improvements in the respiratory domain of the CFQ-R; differences in biomarkers of CFTR activity (sweat chloride) between IVA and placebo groups were also demonstrated. Furthermore, in Study VX11-661-101 dose-dependent

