#### 8.3.5.1 Primary Analysis of the Dose Response trend of absolute change in sweat chloride from baseline through Day 29 (Part 1)

The null hypothesis to be tested is that the dose response of the mean absolute change from baseline through Day 29 for sweat chloride is not decreasing between placebo and the TC dose groups of Part 1, with TC-1A and TC-1B-low pooled. The test will be performed using the MCP procedure with the pre-specified contrasts provided in Section 6.2.2.1, within a linear MMRM framework using PROC GLIMMIX in SAS. The model will include treatment group, visit, and treatment-by-visit interaction as fixed effects, with continuous baseline sweat chloride as a covariate, and will include all data from all treatment groups and visits through Day 29 for analysis. The dose response test will be based on the 1-sided maximum  $t$ -statistic of the individual  $t$ -statistics for the multiple pre-specified contrasts at  $\alpha = 5\%$ , based on the treatment group means through Day 29 (Day 15 and Day 29 only), using an unstructured covariance structure for the within-subject errors. If the model estimation does not converge, a reduced compound symmetry covariance structure will be used instead.

The tabular presentation of results for the average treatment effect across visits, and the treatment effect by visit will be similar to the primary analysis of the primary efficacy variable for Parts 1 and 2. The corresponding  $p$ -value for the decreasing dose response trend will be provided.

In addition, descriptive analyses of the change from baseline will be performed for all treatment groups by post-baseline visit, with TC-1A and TC-1B-low presented both pooled and separately, for descriptive analysis.

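### The Part 1 sweat chloride max-t test controls error at 5% for a flat profile, but not for the stated null of no decreasing dose-response trend, so a significant result does not show that the effect increases with dose

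*Protocol*

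**What the plan says.** Protocol 12.1.2.1 describes the Part 1 procedure as "testing the null hypothesis of the lack of a decreasing dose-response trend versus a decreasing trend", using a one-sided maximum t-statistic "that controls the type I error at alpha = 5"%. Table 12-3 gives the contrasts for (placebo, TC-1B-low, TC-1B-high):

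- linear (1, 0, -1)
- Emax (1, -0.5, -0.5)
- sigmoid Emax (0.5, 0.5, -1)

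Table 12-4 gives power of 95%, 99% and 96% for three profiles, "with a total sample size of 32 subjects in Cohort 1B assigned to TC-1B-high, TC-1B-low, and placebo in the ratio 2:1:1". One of these is the plateau (0, -20, -20).

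Protocol 12.3.4.1 calls it "The test to detect a decreasing dose-response trend of VX-440 at 2 doses in TC with TEZ/IVA relative to placebo". SAP 8.3.5.1 states the null as the dose response of the mean change "for sweat chloride is not decreasing between placebo and the TC dose groups of Part 1", pools TC-1A with TC-1B-low, and reports the p-value as that for the decreasing trend.

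The two TC doses also differ in ivacaftor. Protocol 8.2.2 says "the dose of IVA will be increased from 150 mg q12h to 300 mg q12h when it is administered with VX-440" at 600 mg q12h.

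**The concern.** A 5% test of a null must reject at most 5% of the time wherever that null is true. A null of no decreasing trend includes profiles in which the response improves from placebo to low and then worsens from low to high. It also includes profiles in which neither dose is better than placebo. None of the three contrasts compares high with low alone, and the Emax contrast is simply placebo against the average of the two TC groups. The statistic can therefore be large when the dose ordering is reversed.

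At stake is what Part 1 may be said to show about dose. Protocol 8.2.2 expects dose- and exposure-response information from Part 1 to apply to other populations carrying F508del. A significant p-value labelled as a decreasing trend of VX-440 invites the reading that more VX-440 lowers sweat chloride further.

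**Working it through.** Profiles are mean changes in mmol/L for (placebo, low, high); negative is benefit.

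**Inputs.** SD 13, one-sided 5%, and the contrasts above (Protocol 12.1.2.1, Tables 12-3 and 12-4).
- Cohort 1B: 32 at 2:1:1 gives placebo 8, low 8, high 16; df = 32 - 3 = 29.
- SAP pooling: Cohort 1A (about 10 at 4:1) adds 8 to low and 2 to placebo, giving 10/16/16; df = 42 - 3 = 39.

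**Statistic.** For each contrast c, t = Σ cᵢȳᵢ / (s √Σ(cᵢ²/nᵢ)), and the test uses the largest of the three. The critical value, simulated under (0, 0, 0), is about 2.04 for 8/8/16 and 1.98 for 10/16/16.

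**Reproducing Table 12-4 (8/8/16).** Simulated power is 94.9%, 99.0% and 96.5%, against the stated 95%, 99% and 96%. The test as modelled here is the plan's test.

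**Why reversed profiles reject (8/8/16).**
- Emax contrast SE = 13 × √(1/8 + 0.25/8 + 0.25/16) = 5.39.
- Under (0, -20, -10) the Emax contrast equals 10 + 5 = 15, and 15/5.39 = 2.78, well above 2.04.
- Under (0, -20, 0) it equals 10, and 10/5.39 = 1.86, close to 2.04.
- Sigmoid contrast SE = 13 × √(0.25/8 + 0.25/8 + 1/16) = 4.60. Under (0, +20, 0) the contrast equals 10, and 10/4.60 = 2.18.

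**Rejection rates.**

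| True profile | 8/8/16 | 10/16/16 |
|---|---|---|
| (0, 0, 0) flat | 5% | 5% |
| (0, -20, -10) high has half the low-dose effect | 77% | 88% |
| (0, -20, 0) high inert | 44% | 56% |
| (0, +20, 0) neither dose helps | 56% | 66% |
| (0, -10, 0) high inert, smaller low-dose effect | 15% | 19% |
| (0, -20, -20) plateau | 96% | 99% |

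Under (0, -20, -10), in 75% of all trials (8/8/16) or 87% (10/16/16) the test rejects while the observed high-dose mean is worse than the low-dose mean.

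**What the direct comparison can show.** The 95% CI half-width for high minus low is t(0.975, df) × 13 × √(1/n_low + 1/n_high):
- 8/8/16: 2.045 × 13 × √(1/8 + 1/16) = 11.5 mmol/L
- 10/16/16: 2.023 × 13 × √(1/16 + 1/16) = 9.3 mmol/L

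Under the plan's own (0, -15, -20) the true difference is 5 mmol/L, and this CI excludes zero in about 14% or 19% of trials.

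**The case against.** The best defence is that this is an ordinary max-t signal test, whose working null is a flat profile, and that the plan is open about it. The contrasts are printed, and the comparison is framed relative to placebo. High minus low already falls under the between-group comparisons with 95% CIs promised in Protocol 12.3.4.1 and SAP 8.3.1.1.1, so a reversed ordering would be visible. Protocol 8.2.2 explains the higher ivacaftor dose, and Protocol 12.4.2 plans PK/PD models using VX-440, TEZ and IVA concentrations. The endpoint is secondary, in a Phase 2 study. Redacted text follows the test, and nothing is assumed here about its content.

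Most of that stands, and it rules out several stronger readings that a reader might infer.
- *The plan claims proof that high beats low.* It does not; it speaks of detecting a trend.
- *The test rejects for any TC effect over placebo.* It does not: (0, -10, 0) rejects in only 15% of trials at 8/8/16.
- *Rejecting under the plateau is a false positive.* It is not. With placebo as zero dose, the plateau is a listed target alternative, with its power stated.
- *Rejection can be restated as a TC effect over placebo.* The (0, +20, 0) result contradicts that.
- *TEZ/IVA alone would produce rejection.* The documents give no such effect in this genotype. Protocol 8.2.1 says efficacy of the combination has not been established there.

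The defence does not cure the stated null. It is not written as flat, and no rule links the high-versus-low estimate to the trend conclusion.

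**Conclusion.** The test is sound as a signal test, and its power figures reproduce. The stated null and the label on the p-value are wrong as written: 5% holds at the flat profile, but rejection reaches 77% or 88% when the high dose has half the low-dose effect. The (0, +20, 0) case is extreme and serves only to show that rejection does not guarantee benefit over placebo.

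Attribution is a smaller, related limit. Placebo contains no TEZ/IVA, and ivacaftor differs between the low and high arms, so neither a trend nor its absence belongs to VX-440 dose alone.

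The figures assume one normal summary per subject with SD 13, equal variances, no missing data and no gain from the MMRM covariate. A smaller residual SD would change them, but the contrasts would still not separate high from low.

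**What to change.** In Protocol 12.1.2.1 and 12.3.4.1 and SAP 8.3.5.1:

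1. State the null as a flat profile across placebo and the TC groups.
2. State that a significant max-t result is a dose-response signal, meaning departure from flat toward at least one candidate shape, and does not show that high is better than low.
3. Beside the p-value, report the adjusted TC-high minus pooled TC-low difference and each TC-minus-placebo difference, with 95% CIs from the same MMRM.
4. Allow a statement that the effect increases with dose only if the high-minus-low CI supports it and the high regimen is better than placebo. Both conditions are needed: under (0, +20, 0) the high-minus-low CI alone favours high in 93% (8/8/16) or 99% (10/16/16) of trials.
5. Call the arms TC regimens, and refer attribution to VX-440 to the PK/PD analysis already planned.

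The test, sample size and data collection are unchanged. The cost is wording and a few contrasts from a model already specified. The real price is interpretive: with about 14% or 19% chance of a supporting CI under (0, -15, -20), Part 1 will seldom support a claim that the effect increases with dose.
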